Patients allocated to caliber-15 coiling will preferably receive caliber-15 coils (perhaps including a caliber-15 framing coil (or not), as many Deltamaxx filling coils as safely achievable, but the procedure can be completed with caliber-10 or smaller finishing coils, in order to achieve as complete an occlusion as possible, keeping the procedure as safe as possible.

Patients allocated to caliber-10 coiling will preferably receive caliber-10 coils (perhaps including a caliber-10 framing coil, caliber-10 filling and finishing coils), once more to achieve as complete an occlusion as possible, keeping the procedure as safe as possible.

Both groups will receive platinum coils only. Balloon-assisted or stent-assisted coil embolization is permitted, but should be noted in the procedure CRF.

Technical freedom

The goal of the endovascular procedure is (as usual) to realize the most complete exclusion of the lesion that is judged to be possible, while keeping risks as small as possible, using the randomization algorithm's assigned embolization material. At any time during the procedure the interventionist is unrestricted in the use any device, technique or drug judged important to the safety and success of the endovascular procedure.

If a patient is randomized to 15-caliber coils but the operator prefers, for strong clinical reasons not initially thought of at the time of recruitment, not to deploy predominantly voluminous coils in this particular case, he should proceed using appropriate coils in the best interests of the patient. The converse is also true. In any such case, the operator details reasons on the endovascular treatment case report form. Analysis will be on an intention to treat and per-protocol basis.

Randomization

DELTA is designed with 1:1 randomization.

A minimization algorithm will be used whether the aneurysm is ruptured or unruptured and previously treated or not (major recurrence).

Type, frequency and duration of follow-up

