For the analysis of the safety data, clinical examinations will be recorded at end of procedure, at discharge, and at the time of follow-up imaging (to 12 ± 2months). Follow-up CT-scan or MRI will be performed at 24 hrs or before discharge to detect silent periprocedural events, as standardly performed in each institution. In certain cases, when patients are unable or unwilling to come to the hospital for follow-up visits information may be collected via telephone. Also, Rankin scores may be obtained through phone interviews (using a standardized questionnaire) by the study coordinator or the Principal Investigator.

Adverse events will be recorded immediately after the procedure and during the 12-month follow-up period. First, the number and nature of adverse events for each patient is recorded. Then the relation to the aneurysm itself, to the endovascular coil embolization (not possibly or probably related) will be recorded. Clinical assessments will include the modified Rankin scale (mRS) at 6-12 months. Follow-up imaging studies will be performed at 12 (±2) months by either catheter angiography or non-invasive vascular imaging according to the preference of the participating center. The commonly recommended 6 month follow-up angiogram may not be sufficient to detect most recurrences.³⁸

Table 1: Schedule of Evaluation

Evaluation	Pre-entry	Entry	Treatment	Discharge	6 months	12 ± 2 months
Informed consent		х				
Documentation of	х					
Disease/disorder						
Medical/treatment	х					
history						
Clinical assessment	х		х	х	х	х
Neurological exam	х			x		х
Vascular imaging	х		х			х
Brain imaging	х			x*		
WFNS (for HSA patient)		х				
mRS		х		х	х	х

^{*} According to standard of care of participating centre

Outcomes

Primary outcome

The primary outcome determines the size of the population to be studied to reach statistical significance. Although the clinical significance of angiographic recurrences remains to be determined, the primary outcome cannot be limited to hemorrhagic events, estimated to be quite rare, in the range of 0.1-1% per year. New coils or embolic agents are meant to improve long-term results, including a reduction in the recurrence rate.

Primary endpoint:

The primary efficacy endpoint will mainly consist in the occurrence of a major recurrence or a residual aneurysm at the time of follow-up angiography at 12 (±2) months.

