An independent committee will adjudicate, for each patient, whether he or she has reached the endpoint. In the absence of follow-up imaging, the committee will adjudicate other potential cases of treatment failures (expected to be rare) such as:

- Hemorrhage during the follow-up period
- Retreatment of the same lesion by endovascular or surgical means during the follow-up period
- Occurrence or progression of a mass effect in relation to the treated aneurysm
- Morbidity and mortality that precludes follow-up

The pilot phase of the study was powered to detect a difference of 3% in mean packing density between the 2 groups.

Secondary outcomes:

Secondary outcomes include other indices of immediate treatment success as well as standard safety outcomes:

- Procedure-related serious adverse events
- Initial technical success of the coiling strategy
- Use of adjunct devices.
- Number and total length of coils implanted for each type
- Packing density (core-lab measured)
- Time of fluoroscopic exposure
- Immediate angiographic results according to the Montreal scale

- mRS at 1 year follow-up
- Major recurrence on follow-up angiography
- Morbidity and mortality that precludes angiographic follow-up

Concerning radiographic evidence of recurrence, the angiographers at each participating center will ensure that best projections showing residual necks at the time of treatment are repeated during follow-up evaluations. For the purpose of this study, only major recurrences or residual aneurysms that are of a size that would ideally necessitate retreatment, as judged by the core lab, will be counted. Angiographic results will also be scored according to a previously published classification system¹² as complete obliteration, residual neck or residual aneurysm and groups will be compared initially and at follow-up at 12 ± 2months.

Recurrences will be recorded (present or absent) as they are discovered, at the routine follow-up assessments as clinical symptoms appear any time during the 12 months that follow the intervention. The independent core lab will determine the presence of angiographic recurrences.

Initial technical success

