Descriptive statistics will be done on demographic variables and pre-operative and peri-operative data to compare the two groups at baseline. Means, standard deviations and range will be presented for quantitative variables and frequency tables for categorical variables. Those statistics will be broken down by treatment arm. Comparability of the groups will be assessed through independent ANOVAs (quantitative data) or Mantel-Haentzel and chi-square tests (categorical data). For the pilot phase, the number of patients with satisfactory immediate angiographic results, as well as the mean packing density, will be compared between the 2 groups. The primary outcome of the pivotal phase, recurrence rates (for both intent-to-treat end per-protocol populations) will be compared between groups through a z-test for independent proportions at 6 months and 12 months. Secondary outcomes and safety data will be compared between groups through independent t-tests (quantitative variables) or chi-square statistics (categorical data). The analyses of neurological data at follow-up will control for baseline data when possible (for tests done before discharge and at follow-up) using logistic regression, ANCOVA or Cox regression multivariate models. All tests will be interpreted with adjustment for the interim analysis to have the 0.05 level of confidence at 12 month only. Finally, a logistic regression will be used to find variables capable of predicting recurrences. The method planned is a stepwise forward with alpha < 0.05 to enter a predictor. Possible predictors include the type of the aneurysm, location, size of the aneurysm, size of the neck of the aneurysm as well as other baseline characteristics.

Pilot phase

The pivotal trial will be preceded by a pilot phase of approximately 165 patients designed to verify the feasibility of the coiling strategy, compliance to treatment group allocation, the safety of an 15-caliber platinum coil embolization strategy, recruitment rates, and the capacity to improve packing density with a standardized effect size (E/S) of 0.60, with a power of 95% and a two-sided alpha error of 0.05 (assuming the packing density of the control group will be approximately 25%). The data will be reviewed and analyzed by the DSMC and recommendations will be forwarded to the Steering Committee regarding continuation into the pivotal phase of the study.

Protection against bias

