For ruptured aneurysms, the physician will explain the treatment options including surgery to the patient and relatives. If endovascular treatment is to be offered, the physician will explain the potential benefits of using voluminous coils in terms of reducing the recurrence rate. Following verification that inclusion and exclusion criteria are met, the consent form and voluntary nature of participation into the study will be explained to the patient and relatives. The patient and family will be offered to sign the consent form. At this time, the recruitment form is filled and randomization can proceed online.

7. Randomization is automatic after the registration form is entered.

- 8. Elective patients are scheduled for treatment (within 1-2 months). Ruptured cases are treated as soon as possible as generally done. Images are sent to the coordinating centre.
- 9. For all patients, a procedure form is completed following treatment. Pre and final images, as well as 24 hour or at discharge CT scan, are sent to the coordinating centre.

 Discharge assessment form completed at the time of discharge.
- 10. Severe adverse events are entered online or faxed within 48 hours to the coordinating centre. The coordination center will transmit the information to the clinical adjudication committee which will relay it to the DSMC. These events include haemorrhages, strokes related to the aneurysm, deaths, or further treatments of aneurysm.
- 11. All patients will be followed at 6 and 12 months. Follow-up visits are crucial to assess any change in medical condition and to answer questions.
- 12. For all patients, follow-up visits at 6 and 12 months and vascular imaging 12 (±2) months. Follow-up angiography, catheter or non-invasive, is required. Images are sent to the coordination centre.

Centre requirements

- 1. Participating centres will be regional referral centre for the treatment of intracranial aneurysms. They will have demonstrated a large experience in endovascular treatment of aneurysms (at least 100 patients treated with safety records within acceptable limits (< 8% overall treatment-related complications; < 4% poor outcome at follow-up).
- 2. The names of operators in each centre should be submitted to the coordinating centre. The years of experience and number of aneurysms treated will be kept in a confidential centre log.

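### The primary recurrence outcome is to be tested at 6 months, before any protocol-scheduled follow-up imaging, and the deciding analysis population is not named

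*Combined protocol and SAP*

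**What the plan says.** **Test.** Section 2, Planned analyses, names the primary outcome of the pivotal phase as "recurrence rates (for both intent-to-treat end per-protocol populations") and says that these rates "will be compared between groups through a z-test for independent proportions at 6 months and 12 months". The same paragraph adds: "All tests will be interpreted with adjustment for the interim analysis to have the 0.05 level of confidence at 12 month only".

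**Endpoint.** Section 2, Primary endpoint, defines it mainly as the "occurrence of a major recurrence or a residual aneurysm at the time of follow-up angiography at 12 (±2) months". The core lab judges recurrence from images.

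**Imaging schedule.** In Table 1 the 6-month column has a clinical assessment and the modified Rankin scale, but no vascular imaging. Section 4, DELTA treatment plan, item 12, requires "follow-up visits at 6 and 12 months and vascular imaging 12 (±2) months". The follow-up section of Section 2 comments: "The commonly recommended 6 month follow-up angiogram may not be sufficient to detect most recurrences".

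**Early events.** Under Secondary outcomes: "Recurrences will be recorded (present or absent) as they are discovered, at the routine follow-up assessments". Where follow-up imaging is absent, a committee adjudicates clinical failures (hemorrhage, retreatment, mass effect, and morbidity or mortality that prevents follow-up), which the protocol expects to be rare.

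**Populations.** Section 2, Technical freedom: "Analysis will be on an intention to treat and per-protocol basis". No section makes either population primary. Initial technical success gives one deviation threshold, less than 30% of coil length being 15-caliber, and it applies to the 15-caliber arm only.

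**The concern.** A test of recurrence needs each patient's recurrence status at the time of the test. At 6 months the protocol provides no image from which the core lab could determine it. A statistician who follows the plan literally must either count patients without an image as recurrence-free or restrict the comparison to those who happen to have one. The plan does not choose between these, and neither gives the 6-month recurrence rate. A null or a chance difference could then be read as early evidence about the coils.

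The second issue is which result decides the trial. Technical freedom lets operators depart from the allocated coil type in either direction, so the ITT and per-protocol results may differ. With no ranking, the choice between them could be made after both are known. Because the only stated threshold applies to one arm, per-protocol exclusions could also be lopsided.

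**Working it through.** **1. The plan's own figure.** Inputs from Section 2, Sample size and Table 2: 33% against 20%, 256 per arm, two-sided 0.05, Fisher's exact test, stated power 0.9009. Exact enumeration gives 0.903, so the figure reproduces. The z-test named in Planned analyses has exact power 0.919 at 256 per arm. All of this concerns the 12-month endpoint. The plan gives no 6-month rate or power.

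**2. What is available at each planned test.**

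| | 6 months | 12 (±2) months |
|---|---|---|
| Visit (treatment plan, items 11 and 12) | yes | yes |
| Clinical assessment and Rankin scale (Table 1) | yes | yes |
| Vascular imaging (Table 1; item 12) | not scheduled | scheduled |
| Primary endpoint defined | no | yes |
| z-test planned (Planned analyses) | yes | yes |

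The imaging window opens at 12 − 2 = 10 months, four months after the 6-month visit.

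**3. What a 6-month test would measure.** Let π be the true proportion with recurrence, and let q1 and q0 be the probabilities of an early image in patients with and without recurrence. Leave clinical failures aside.

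- Patients without an image counted as recurrence-free: observed rate = π × q1.
- Imaged patients only: observed rate = π × q1 / [π × q1 + (1 − π) × q0].

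The first equals π only if every patient with recurrence is imaged. The second equals π only if imaging is unrelated to recurrence. For illustration, take π = 0.33, the 12-month control rate, borrowed because no 6-month rate is given. The imaging probabilities are assumptions.

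- q1 = q0 = 0.20: the first rule gives 0.33 × 0.20 = 0.066; the second gives 0.33.
- q1 = 0.40, q0 = 0.20: the first gives 0.33 × 0.40 = 0.132; the second gives 0.132 / (0.132 + 0.67 × 0.20) = 0.132 / 0.266 = 0.496.

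The same underlying 33% appears as anything from about 7% to 50%, depending on who is imaged and how the others are counted.

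**4. Two unranked populations.** Suppose a fraction e of each arm is excluded at random from the per-protocol set (assumption). Under the null the two z statistics have correlation ρ = √(1 − e). The chance that at least one is significant is 1 − P(|Z1| < 1.96 and |Z2| < 1.96), taken from the bivariate normal distribution.

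| e | ρ | False-positive rate if either could count |
|---|---|---|
| 5% | 0.975 | 0.060 |
| 10% | 0.949 | 0.065 |
| 15% | 0.922 | 0.068 |

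A simulation with 33% in both arms and 256 per arm (400,000 runs) gave the same three values. The excess over 5% is 1.0 to 1.8 percentage points. Non-random exclusion would add bias that this calculation does not capture.

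**The case against.** The strongest reply is that the decisive time point is not in doubt. The hypothesis and the endpoint are both set at 12 months, and Planned analyses keeps the 0.05 level for that time alone. The 6-month test therefore cannot decide the trial. This stands, and it limits the point: a reader might infer that a second test of the primary outcome inflates the type I error, but the text does not support that. The reserved level does not, however, say what data the 6-month test would use. Treating that test as the interim analysis does not help either, because no scheduled image exists by then.

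A second reply is that the protocol calls the 6-month angiogram commonly recommended, so some centres may image routinely at that time. This also stands in part. One cannot say that early images would come only from selected or symptomatic patients, because the documents are silent on centre practice. What can be said is that the protocol schedules none and so guarantees no status for the remaining patients.

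A third reply is that no section allows either population to be declared the answer, and that ITT is named first. The first part is true, which is why the calculation in step 4 is conditional. Order of mention is not a rule, though, and nothing in the text settles a disagreement between the two.

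**Conclusion.** The concern holds as an inconsistency in the analysis plan. The plan calls for a 6-month test of an imaging outcome for which it schedules no follow-up image before month 10, and by its own account a 6-month angiogram may miss most recurrences. The 12-month design and its sample size are unaffected.

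It is tempting to express the defect as low power at 6 months. The documents do not support such a figure: they give no 6-month rate, and any power computed on 256 per arm would assume that every patient's status is known, which is exactly what is lacking. Nor do they show that early imaging would differ by arm, although operators know the allocation.

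The population point is real but smaller: about 1 to 2 percentage points of false-positive rate under random exclusion, and only if either result could be declared the answer. Overall the plan should be corrected, but the trial's main comparison is not undermined.

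**What to change.** In Section 2, Planned analyses:

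- Delete the 6-month test of the primary outcome. Report clinical failures and any recurrences discovered up to 6 months descriptively, by arm, with the number of patients imaged.
- State that the single primary analysis is the adjudicated endpoint at 12 (±2) months in the ITT population, at an overall two-sided 0.05 after any interim adjustment. The adjustment must stay in the wording, because the plan refers to an interim analysis and the monitoring committee's terms let it set how often such analyses are made.
- Make the per-protocol analysis supportive. Write an exclusion rule that covers both arms and fix it before any outcome comparison by arm. Fixing it before unblinding is not precise enough, because operators and research teams know the allocation. The number and length of coils by type are already collected, so the rule needs no new data.
- State how patients with no coils deployed are counted in the ITT analysis, since Appendix 3 lists that event as an end of study.

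The cost is wording only: no added patients, visits, imaging or data items. What is given up is an early test that has no scheduled imaging data behind it.

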Classic biases such as selection bias or information bias will be dealt with by randomizing patients and blinding in the assessment of the primary outcome. Random allocation of treatment is best for insuring internal validity and is the best approach to control for confounding and selection bias.

Finally, control variables will be measured and compared between treatment groups in order to ensure group comparability (initial angiographic success, periprocedural events, and disease characteristics). Protocol compliance will be carefully monitored in every centre.

Publication of research findings

Publication of the results of this trial will be governed by the policies and procedures developed by the Steering Committee (SC). Any presentation, abstract, or manuscript will be made available for review by the SC prior to submission.

Regulatory considerations

The study will only start after approval by the Institutional Review Board/Institutional Ethics Committee (IRB/IEC) of each centre. The study will be performed in accordance with the national regulatory requirements of each participating centre. Participants will be fully aware of the study purposes, the procedure and the risks of each intervention. When signing the study consent form, they will be informed that participation is voluntary and they can request to be withdrawn from the study at any time. Patient enrolment in this trial will comply with the principles enunciated in this Declaration of Helsinki*. All the information collected with the questionnaires will be kept confidential and will be used on an anonymous basis.

* The Declaration of Helsinki (Document 17.C) is an official policy document of the World Medical Association, the global representative body for physicians. It was first adopted in 1964 (Helsinki, Finland) and revised in 1975 (Tokyo, Japan), 1983 (Venice, Italy), 1989 (Hong Kong), 1996 (Somerset-West, South Africa) and 2000 (Edinburgh, Scotland). Note of clarification on Paragraph 29 added by the WMA General Assembly, Washington 2002.

Trial management and coordination

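### Allocation is minimised on rupture status and previous treatment, but the primary z-test ignores both; if they predict recurrence, the test is conservative and gives up a little power

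*Combined protocol and SAP*

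**What the plan says.** Section 2, Randomization: "DELTA is designed with 1:1 randomization", and "A minimization algorithm will be used whether the aneurysm is ruptured or unruptured and previously treated or not (major recurrence".

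Section 2, Planned analyses: the primary outcome of the pivotal phase, in both the intention-to-treat and per-protocol populations, is "compared between groups through a z-test for independent proportions". No stratification or covariate is named for it. Three other methods in that section might seem to fill the gap, but none does:

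- Mantel-Haenszel is named only for checking whether the groups are comparable.
- Covariate adjustment is planned for a different outcome: "The analyses of neurological data at follow-up will control for baseline data when possible".
- The logistic regression on recurrence is a forward stepwise search for predictors. It names no treatment term.

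Two statements bear on the smaller point. Planned analyses says "Descriptive statistics will be done on demographic variables and pre-operative and peri-operative data to compare the two groups at baseline". Protection against bias says that control variables will be "compared between treatment groups in order to ensure group comparability (initial angiographic success, periprocedural events, and disease characteristics". Section 2, Secondary outcomes, lists "Immediate angiographic results according to the Montreal scale" and "Procedure-related serious adverse events" as outcomes.

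**The concern.** Minimisation removes most of the chance imbalance between arms on the two factors. The variance in the two-sample z-test still allows for that imbalance, because it is derived for simple randomisation. When the factors are related to recurrence, the standard error therefore overstates the real sampling variation of the difference. The p-value is then too large on average, and any interval built on the same standard error is too wide. The main result would not reflect how patients were allocated, and some power already paid for in the design would go unused. There is no risk of excess false positives.

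The wording on comparability is a separate matter. Initial angiographic success, periprocedural events and peri-operative data arise after randomisation, and the coils can affect them. If they are tabulated as evidence that the groups started alike, a real coil effect could be read as baseline imbalance. The documents do not plan to adjust for them, so this is about interpretation only.

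**Working it through.** **The plan's own figure.** Sample size and Table 2 give 256 per arm, 33% v 20%, two-sided Fisher's exact test, alpha 0.05, power 0.9009. Full enumeration of that test gives 0.903, so the figure reproduces. The total of 564 is 512 × 1.1 = 563.2, rounded up to an even number.

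**Power of the z-test that will be used**, at 256 per arm under simple randomisation:

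- Pooled rate (0.33 + 0.20)/2 = 0.265; null SE = √(2 × 0.265 × 0.735/256) = 0.0390
- Alternative SE = √((0.33 × 0.67 + 0.20 × 0.80)/256) = 0.0386
- Power = Φ((0.13 − 1.96 × 0.0390)/0.0386) = Φ(1.39) = 91.7%

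**Assumptions (not in the documents).** 50% ruptured, 15% previously treated, factors independent, treatment odds ratio common across cells, and marginal rates held at 33% and 20%. Cell shares are then 42.5, 42.5, 7.5 and 7.5% for unruptured/new, ruptured/new, unruptured/previous and ruptured/previous.

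**Formula.** Let R² be the share of outcome variance explained by the cells: R² = Σ wᵢ(pᵢ − 0.33)² / (0.33 × 0.67). Under the null with allocation balanced on the cells:

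- SE excess of the z-test = 1/√(1 − R²) − 1
- True alpha = 2Φ(−1.96/√(1 − R²))

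Minimisation on marginal totals balances the cells only approximately, so the formula is a check on the simulation below.

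**Worked example: moderate factors** (odds ratio 2 for rupture, 3 for previous treatment). The cell rates that average 33% are 0.2214, 0.3626, 0.4604 and 0.6305.

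- Numerator = 0.425 × 0.1086² + 0.425 × 0.0326² + 0.075 × 0.1304² + 0.075 × 0.3005² = 0.0135
- R² = 0.0135/0.2211 = 0.061
- SE excess = 1/√0.939 − 1 = 3.2%
- True alpha = 2Φ(−2.02) = 0.043

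**Simulation.** 564 patients, minimisation on the marginal totals with an assumed biased coin of 0.8, 10% random loss, and the pooled z-test against a Cochran-Mantel-Haenszel (CMH) test over the four cells without continuity correction. There were 100,000 null runs (Monte Carlo SE 0.0007) and 40,000 power runs (SE about 0.0013).

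| Factors (OR rupture, OR previous treatment) | Control rates by cell, % | R² | SE excess | Alpha by formula | Simulated alpha, z / CMH | Power %, z / CMH |
|---|---|---|---|---|---|---|
| None (1, 1) | 33/33/33/33 | 0 | 0% | 0.050 | 0.050 / 0.050 | 91.8 / 91.7 |
| Mild (1.5, 1.5) | 27/36/36/46 | 0.014 | 0.7% | 0.048 | 0.048 / 0.049 | 91.9 / 92.0 |
| Moderate (2, 3) | 22/36/46/63 | 0.061 | 3.2% | 0.043 | 0.044 / 0.050 | 92.1 / 92.8 |
| Strong (3, 6) | 17/38/55/78 | 0.140 | 7.9% | 0.035 | 0.037 / 0.051 | 92.9 / 94.8 |

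**Second simulation.** 512 analysed patients, 10,000 runs per scenario, Monte Carlo error about 0.002 on alpha and 0.003 on power. Rupture prevalence was 50% and previous treatment 10 to 20%.

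| OR rupture, OR previous treatment | Alpha, z / CMH | Power %, z / CMH |
|---|---|---|
| 1, 1 | 0.049 / 0.048 | 91.7 / 91.7 |
| 2, 2 | 0.045 / 0.048 | 92.3 / 92.7 |
| 2, 4 | 0.044 / 0.052 | 92.1 / 93.0 |
| 3, 5 | 0.039 / 0.053 | 93.3 / 95.0 |

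Direction and size agree with the first simulation.

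**Sensitivity to the share previously treated.** With 5% instead of 15%, the null SE excess falls from 3.2% to 2.0% (moderate) and from 7.9% to 4.9% (strong).

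**The case against.** The strongest objection is that little follows from this. The z-test never inflates type I error and its power stays above 90% in every scenario. The gain from stratifying is 0.1 point with mild factors and 0.7 with moderate ones. It reaches 1.9 only when control recurrence runs from 17% to 78% across cells. All of this rests on prevalences, odds ratios and a minimisation probability that the documents do not state. This stands. It limits how much weight the point carries, but it does not make the unadjusted test the better choice.

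Planned analyses names no confidence interval for the primary outcome, so a claim about its width applies only if one is reported from the z-test variance. That also stands. The excess under the design alternative is close to the null figure. For moderate factors, the summed within-cell variances are 0.2076 + 0.1518 = 0.3594 against 0.2211 + 0.1600 = 0.3811 ignoring the cells, and √(0.3811/0.3594) − 1 = 3.0%.

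A sponsor might point to the stepwise logistic regression on recurrence, whose candidates include aneurysm type and other baseline characteristics and could take in both factors. It does not close the gap: it names no treatment term, and entry at p < 0.05 does not guarantee that either factor is kept.

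Adjustment also has some cost. An adjusted odds ratio is conditional on the factors and is not the difference in proportions used for sizing, and sparse cells need a rule. Both can be settled in the wording.

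Finally, the comparability wording has nothing to do with minimisation, and the documents already treat the overlapping measures as secondary outcomes. It is a separate, minor correction and adds no weight to the main point.

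**Conclusion.** The concern holds as stated. The plan balances on two factors and then leaves them out of the primary comparison. If they predict recurrence, the z-test is conservative: its true alpha is about 0.048 for mild, 0.044 for moderate and 0.037 for strong effects, and it gives up roughly 0 to 2 points of power against a stratified test. If they do not, the two tests perform alike. These sizes depend on the assumed prevalences, odds ratios and biased-coin probability set out above; the direction depends only on whether the factors are prognostic. The trial remains valid and adequately powered without the change. It should be made all the same, because it aligns the analysis with the allocation and fixes in advance which result is primary.

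**What to change.** In Planned analyses, make the primary intention-to-treat comparison at 12 months account for rupture status and previous treatment. Name one of these in advance:

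- a CMH test with a stratified risk difference and 95% CI; or
- logistic regression on treatment and the two factors, with a standardised risk difference and 95% CI.

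State that if any factor combination has very few patients, the two factors enter as main effects only. Keep the unadjusted z-test as a sensitivity analysis. Adding aneurysm and neck size is optional.

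In Planned analyses and Protection against bias, limit comparability checks to variables measured before randomisation, and report angiographic success and periprocedural events only as outcomes.

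The cost is wording in the analysis section. No new data are needed: minimisation requires both factors, so they are known for every randomised patient.
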